### 8.3 Off-Agent/Off-Study

Each participant has the right to withdraw from treatment or from the study at any time without prejudice.

#### 8.3.1 Off-Agent Criteria

Participants may stop taking study agent for one or more of the following reasons: completed the protocol-prescribed intervention, adverse event (AE) or serious adverse event (SAE), inadequate agent supply, refusal to continue with study procedures, the need for contraindicated concomitant medications, medical contraindication, disease progression, death or treating physician decision.

Date and reason off-agent should be documented on the Off Agent case report form. Reasons that are not specified on the form should be coded as 'Other' and a brief description provided. Patients who go off-agent must be followed for adverse events (AEs) for at least 30 days from their last treatment.

Note that participants who go off-agent should be encouraged to stay in the study and provide data at the regularly scheduled visits. Local NCORP site staff should complete the study assessment with the patient, especially the neurocognitive and PROs testing and toxicity assessments. LabCorp samples do not need to be collected once the patient is "Off Agent.". Local institutional labs can be used to assess the participant after they are off Ramipril.

#### 8.3.2 Off-Study Criteria

Participants may go 'off-study' for one or more of the following reasons: the protocol intervention and any protocol-required follow-up period is completed, AE/SAE, lost to follow-up, refusal to continue with study procedures, the need for contraindicated concomitant medication, medical contraindication, disease progression, withdraw consent, death, determination of ineligibility (including screen failure), pregnancy, or treating physician decision.

Note that a participant is not automatically taken off-study if they refuse further treatment. In fact, these participants should be encouraged to remain in the study and provide data at their regularly scheduled visits. Date and reason off-study should be documented on the Off Study case report form. Reasons that are not specified on the form should be coded as 'Other' and a brief description provided.

A final evaluation of the participant should be performed when he/she withdraws from the study. If a patient decides to discontinue participation in study at any time prior to study completion, the entire battery of neurocognitive tests and forms should be administered, using the next Neurocognitive and PRO booklet they would have received as well as, all other items in the Schedule of Events (Section 7.1) for the visit.

### 8.4 Study Termination

NCI, DCP as the study sponsor has the right to discontinue the study at any time.

## 9.0 SPECIMEN MANAGEMENT

A single blood draw will be made at the baseline visit. DNA will be isolated from whole blood for APOE genotyping, collected in one (8 ml max) yellow-top Vacutainer tubes (with citrate as the preservative). Samples will be sent to WFUHS for storage and processing.

### 9.1 Sample Processing

Blood samples received from all sites will be brought to the Wake Forest Center for Genomics and Personalized Medicine Research laboratories, where they will be entered into a database and the DNA isolated. DNA from whole blood will be isolated using the AutoPure LS instrument (Qiagen, Inc.).

SNP genotyping of the APOE haplotype will be performed in the Center for Genomics and Personalized Medicine Research at Wake Forest using the iPLEX SNP genotyping system (Sequenom, Inc.), which has been successfully tested and fully integrated into our laboratory. The APOE haplotype will be determined by genotyping the two individual SNPs that make up the haplotype, rs429358 and rs7412, in each individual. Genotypes will be scored using the SpectroTyper software (Sequenom, Inc.), and quality control parameters (e.g., CEPH DNA samples, negative controls) will be determined. Problem samples or SNPs will be reviewed and repeated if necessary.

### 9.2 Site Collection and Handling Procedures

APOE genotype will be derived from approximately 8 ml of whole blood sample taken from a vein in the arm/central line at baseline, at each NCORP site of study enrollment. Prepared shipping kits will be sent to participating NCORP sites from the Wake Forest Biotech Laboratory, who will provide sample handling, storage, tracking, and logistics.

### 9.3 Shipping Instructions

#### Initial Shipping Kits:

Sites should request shipping kits at the time of study approval in advance of putting patients on study and should use the Specimen Kit Request Form (Appendix E). This form should be emailed ([contact]) or faxed to Wake Forest NCORP Research Base at [contact].

#### Additional Shipping Kits:

If additional kits are needed, sites should email the Specimen Kit Request Form directly to the Wake Forest NCORP Biospecimen Laboratory using their email ([contact]). For additional details refer to Appendix E.

## 10.0 ADVERSE EVENTS REPORT REQUIREMENTS

**DEFINITION:** Adverse event (AE) refers to any untoward medical occurrence associated with the use of a drug in humans, whether or not considered drug related. An AE can therefore be any unfavorable and unintended sign, symptom, or disease temporally associated with participation in a study, whether or not related to that participation. This includes all deaths that occur while a participant is on a study.

Please note that all abnormal clinical laboratory values that are determined to be of clinical significance based on a physician's assessment are generally considered AEs, and may need to be reported as per

instructions in Section 10.3 below. Those labs determined to be of no clinical significance or of unknown clinical significance (per the physician's assessment) generally not reported as AEs. Any lab value of unknown clinical significance should continue to be investigated/followed-up further for a final determination, if possible.

A list of AEs that have occurred or might occur can be found in Section 6.2 Reported Adverse Events and Potential Risks, as well as the manufacturer's package insert.

## **10.1 Adverse Events (AEs)**

### **10.1.1 Reportable AEs**

Following the guidance in Section 10.3, any reportable AEs that occur after the informed consent is signed and baseline assessments are completed should be recorded on the REDCap AE CRF whether or not related to study agent, as detailed below.

**The prompt reporting of adverse events is the responsibility of each investigator engaged in clinical research, as required by Federal Regulations**

### **10.1.2 AE Data Elements**

The following data elements are required for AE reporting.

- AE verbatim term
- NCI Common Terminology Criteria for Adverse Events version 5.0 (CTCAE v5.0) AE term (MedDRA lowest level term)
- CTCAE (MedDRA) System Organ Class (SOC)
- Event onset date and event ended date
- Treatment assignment code (TAC) at time of AE onset
- Severity grade
- Attribution to study agent (relatedness)
- Whether or not the event was reported as a SAE
- Whether or not the subject dropped due to the event
- Outcome of the event

### **10.1.3 CTCAE term (AE description) and Grade**

The descriptions and grading scales found in the revised NCI Common Terminology Criteria for Adverse Events (CTCAE) version 5.0 will be utilized for AE reporting. All appropriate treatment areas should have access to a copy of the CTCAE version 5.0. A copy of the CTCAE version 5.0 can be downloaded from the CTEP web site

[http://ctep.cancer.gov/protocolDevelopment/electronic\\_applications/ctc.htm](http://ctep.cancer.gov/protocolDevelopment/electronic_applications/ctc.htm).

Identify the AE using the CTCAE version 5.0. The CTCAE provides descriptive terminology (MedDRA lowest level term) and a grading scale for each AE listed. AEs that do not have a corresponding CTCAE term will be assessed according to the general guidelines for grading used in the CTCAE v5.0. as stated below.

**CTCAE v5.0 general severity guidelines:**

GRADE	SEVERITY	DESCRIPTION
1	Mild	Mild; asymptomatic or mild symptoms; clinical or diagnostic observations only; intervention not indicated.
2	Moderate	Moderate; minimal, local or noninvasive intervention indicated; limiting age-appropriate instrumental activities of daily living (ADL).*
3	Severe	Severe or medically significant but not immediately life-threatening; hospitalization or prolongation of hospitalization indicated; disabling; limiting self-care ADL.**
4	Life-threatening	Life-threatening consequences; urgent intervention indicated.
5	Fatal	Death related to AE.

\*Instrumental ADL refers to preparing meals, shopping for groceries or clothes, using the telephone, managing money, *etc.*

\*\*Self-care ADL refers to bathing, dressing and undressing, feeding self, using the toilet, taking medications, and not bedridden.

**10.1.4 Assessment of Relationship of AE to Treatment**

The possibility that the AE is related to study agent will be classified as one of the following attribution: Unrelated, Unlikely, Possible, Probable, Definite.

**Attribution:** An assessment of the relationship between the adverse event and study agent/intervention, using the following categories.

ATTRIBUTION	DESCRIPTION
Unrelated	The AE is clearly NOT related to the study agent (or product)/intervention
Unlikely	The AE is doubtfully related to study agent /intervention
Possible	The AE may be related to study agent/intervention
Probable	The AE is likely related to study agent/intervention
Definite	The AE is clearly related to study agent/intervention

**10.1.5 Follow-up of AEs**

Any reportable AEs, including lab abnormalities that in the opinion of the investigator are clinically significant, will be followed according to good medical practices and documented as such.

**10.2 Serious Adverse Events (SAEs) [Reporting Overview]**

**DEFINITION:** Serious Adverse Event (SAE) is defined by regulation 21 CFR §312.32 as any adverse

medical event (experience) that results in at least one of the outcomes listed below:

- Death
- Life-threatening
- Results in inpatient hospitalization or prolongation of existing hospitalization for  $\geq 24$  hours.
- A persistent or significant incapacity or substantial disruption of the ability to conduct normal life functions.
- A congenital anomaly/birth defect.
- Important medical events that may not be immediately life-threatening or result in death or hospitalization should also be considered serious when, based upon appropriate medical judgment, they may jeopardize the patient and may require intervention to prevent one of the other outcomes.

**Hospitalization (or prolongation of hospitalization):** For AE reporting purposes, a hospitalization is defined as an inpatient hospital stay equal to or greater than 24 hours.

### 10.3 Reporting of Adverse Events (AEs) for WF-1801

Any reportable adverse event, as defined below, whether observed by study staff or investigator, elicited from or volunteered by the participant, should be documented. Each reportable adverse event will include the date of onset, date of resolution, severity, and the relationship to the study agent or intervention, and any action taken with respect to the study agent or intervention. Please review the chart and instructions below to determine, which AEs are reported for WF-1801.

#### Reasons for Not Reporting All Adverse Events

- Ramipril is a widely used medication taken routinely for high blood pressure on an outpatient basis. Side effects are well documented.
- Because Ramipril is widely used and its toxicity profile is well established, we feel the likelihood of Ramipril increasing standard treatment-related toxicities is low. By not collecting all AEs, we hope to expend our efforts in identifying toxicities that are unexpected and related to Ramipril.

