## 6. PHARMACEUTICAL INFORMATION

### 6.1 Ramipril (IND-Exempt)

#### IND Status

The risks associated with Ramipril are not significantly increased in the proposed study population. The major risk of Ramipril in the non-hypertensive population is hypotension (11%). Ramipril has been used to treat several conditions in non-hypertensive patients including heart failure, post-myocardial infarction prophylaxis, and diabetic nephropathy and has been found to be safe in these settings. Furthermore, Ramipril is a generically available drug, and we are not conducting the proposed study in order to change the labelling instructions for Ramipril. A 10 mg dose of Ramipril was administered in 1,048 hypertensive and normotensive patients at risk of cardiovascular events and tolerability was generally considered to be good to excellent. The HOPE study was a randomized trial of 10 mg dose of Ramipril vs placebo for cardioprevention in over 9500 patients in which 50% of the study population was normotensive at the beginning of the study. A recent analysis of 160 patients treated with GBM at Wake Forest showed no difference in survival in patients treated with ACE inhibitors as compared to patients who were not treated with ACE inhibitors. As such, the risks associated with Ramipril are not significantly increased in the study population and therefore, an IND is not required.

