#### Adverse Events (AEs) to be reported for WF-1801

- **Grade 3:** Any **unexpected** adverse events (AEs) **grade 3** that have an attribution to the intervention of **Possible, Probable or Definite** should be reported.
- **Grade 4:** Any **unexpected** adverse events (AEs) **grade 4** should be reported.
- **Grade 5:** All adverse events (AEs) **grade 5** should be reported.

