#### Methods and Timing of Reporting Adverse Events

**Please refer to the chart below for method(s) of reporting.**

- **All reportable adverse events** will be reported to the Wake Forest NCORP Research Base using REDCap Adverse Event Reporting.

- **Non-expedited Reporting:** Adverse events not requiring expedited reporting through CTEP-AERS should be entered into REDCap within 10 calendar days of learning of the event.
- **Expedited Reporting:** See Section 10.4 for CTEP-AERS expedited reporting.
- Site staff and/or Principal Investigators will also notify WF NCORP Research Base via REDCap reporting and report to CTEP-AERS within 24 hours of discovering the details of all **unexpected (possible, probable and definite) severe, life-threatening (grade 4) and all (expected or unexpected) fatal adverse events (grade 5).**
- All recorded adverse events reported to the Wake Forest NCORP Research Base will be reviewed by the Wake Forest NCORP Research Base Data and Safety Monitoring Committee (DSMC) and will be included in statistical reports to the Wake Forest NCORP Research Base Data and Safety Monitoring Board (DSMB).

Adverse Events								
	Grade 1 & 2		Grade 3		Grade 4		Grade 5	
	Expected	Unexpected	Expected	Unexpected	Expected	Unexpected	Expected	Unexpected
Unrelated						REDCap	REDCap & CTEP-AERS	REDCap & CTEP-AERS
Unlikely						REDCap	REDCap & CTEP-AERS	REDCap & CTEP-AERS
Possible				REDCap		REDCap & CTEP-AERS	REDCap & CTEP-AERS	REDCap & CTEP-AERS
Probable				REDCap		REDCap & CTEP-AERS	REDCap & CTEP-AERS	REDCap & CTEP-AERS
Definite				REDCap		REDCap & CTEP-AERS	REDCap & CTEP-AERS	REDCap & CTEP-AERS

The Wake Forest NCORP Research Base Multi-PI(s), the Wake Forest NCORP Research Base DSMC and/or Study Chair will take appropriate action to inform the membership and statistical personnel of any protocol modifications and/or precautionary measures, if this is warranted.

Institutions must comply with their individual Institutional Review Board (IRB) policy regarding submission of documentation of adverse events. All CTEP-AERS reports should be sent to the local IRB in accordance with the local IRB policies.

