## **12.7 Evaluation of Toxicity**

### **Evaluation of Toxicity and Adverse Effects of Ramipril**

All patients will be evaluable for toxicity from the time of their first treatment with Ramipril. Toxicities will be quantified using the CTCAE v5.0 for Toxicity and Adverse Event Reporting. Fisher exact tests will be used to assess treatment differences in the incidence of individual toxicities, and logistic regression will be used to assess treatment differences in the incidence of any grade 3 or higher toxicity possibly, probably or likely related to Ramipril adjusting for baseline patient characteristics. In order to rule out cytoprotection of tumor by Ramipril, response rates will be compared to historical controls from RTOG 0825.

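### Expected Grade 3–4 events related to Ramipril are not reportable, so they need not reach the adverse event form or the monthly DSMC review, and 12.7 does not name another source for its toxicity rate

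*Combined protocol and SAP*

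**What the plan says.** Section 10.3 sets three reporting rules. For Grade 3: "Any unexpected adverse events (AEs) grade 3 that have an attribution to the intervention of Possible, Probable or Definite should be reported". For Grade 4: "Any unexpected adverse events (AEs) grade 4 should be reported". For Grade 5: "All adverse events (AEs) grade 5 should be reported". The chart in 10.3 agrees with this text, and every cell for an expected Grade 3 or Grade 4 event is blank. The expedited table in 10.4 leaves expected Grade 4 blank and has no Grade 3 column.

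The stated reason is that Ramipril is widely used with a well-documented profile: "By not collecting all AEs, we hope to expend our efforts in identifying toxicities that are unexpected and related to Ramipril".

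No section defines expected. The nearest pointer is in 10.0: "A list of AEs that have occurred or might occur can be found in Section 6.2 Reported Adverse Events and Potential Risks", together with the package insert. Section 6.2 lists, among others, hypotension, syncope, angioneurotic edema, acute renal failure, hepatic failure, pancytopenia and convulsions.

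Under 10.1.1 it is reportable AEs that go on the REDCap AE form. Section 10.3 adds: "All recorded adverse events reported to the Wake Forest NCORP Research Base will be reviewed by" the DSMC, and that these events also enter the statistical reports to the DSMB. Section 11.4 describes the monthly DSMC review as one of reportable AEs and protocol deviations.

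Section 12.7 plans a logistic regression on the incidence of "any grade 3 or higher toxicity possibly, probably or likely related to Ramipril". It sets no limit by expectedness and names no form as its source.

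**The concern.** The filter works on expectedness before relatedness. An unexpected Grade 4 event judged unrelated to Ramipril must be entered. A Grade 4 angioedema or renal failure judged definitely due to Ramipril need not be, if it is classed as expected from Section 6.2 or the package insert.

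Two things are at stake. First, the DSMC is the only body that looks at events monthly, and several related Grade 3–4 events of a known kind could occur without appearing in its review. Second, this pilot is meant to inform a randomized trial, and the rate of related Grade 3 or higher toxicity is one of its natural outputs. The profile in 6.2 comes from hypertension, heart-failure and cardiovascular-risk populations, not from patients on brain radiotherapy with temozolomide. The belief in 10.3 that added toxicity is unlikely is therefore something the trial could check, and the filter removes part of the data for doing so.

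**Working it through.** **Inputs.** The 10.3 rules and chart; the 10.4 expedited table; the AE form rule in 10.1.1; the DSMC remit in 11.4; the 12.7 analysis; the 7.1 schedule and 7.3 text; N = 75 from 12.2.

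**Denominator.** The plan's sample size reproduces. For 65% against 80%, one-sided 0.05 and 90% power:
n = [(1.645 × √(0.65 × 0.35) + 1.282 × √(0.80 × 0.20)) / 0.15]² = 74.78, rounded up to 75. The point uses this figure only as a denominator.

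**Chart tally.** Is any report required?

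| Attribution | G3 expected | G3 unexpected | G4 expected | G4 unexpected | G5 expected | G5 unexpected |
|---|---|---|---|---|---|---|
| Unrelated, Unlikely (2 rows) | no | no | no | yes | yes | yes |
| Possible, Probable, Definite (3 rows) | no | yes | no | yes | yes | yes |

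- Expected Grade 3–4: 5 rows × 2 columns = 10 cells, 0 reportable.
- Related Grade 3 and above: 3 rows × 6 columns = 18 cells, 3 × 4 = 12 reportable.
- The missing 18 − 12 = 6 cells are expected Grade 3 and expected Grade 4 at the three related attributions.

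**Does serious status rescue them?** No. Section 10.2 defines a serious event, but 10.4 sends forward only serious events that meet its own table. A related, expected Grade 3 hospitalisation meets neither the 10.3 chart nor the 10.4 table.

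**What 12.7 would see.** I read its attribution terms as the Possible, Probable and Definite categories of 10.1.4. If the rate were built from the AE form, a patient whose only related Grade 3 or higher event was expected and non-fatal would count as event-free, whatever the true rate.

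**How many events might this be?** The documents give no Grade 3–4 rate for Ramipril, so the following rates are assumptions. With true rate p, the expected number of patients is 75p and the chance of at least one is 1 − (1 − p)^75.

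| Assumed p | Expected patients in 75 | Chance of at least one |
|---|---|---|
| 1% | 0.75 | 53% |
| 2% | 1.5 | 78% |
| 5% | 3.75 | 98% |

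At each rate, the number that the AE rules require to be entered is zero.

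**The other route.** Section 7.3 has the study team assess toxicity from Week 1 to 5 months after radiotherapy, and Section 3 also describes toxicity checks at months 2 to 5. The 7.1 schedule marks the Toxicity Assessment row only to Week 10. Ramipril continues to Week 22, so on the schedule 22 − 10 = 12 weeks of dosing, plus the follow-up to Week 26, carry only the filtered Adverse Event Reporting row.

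**The case against.** The best defence is that toxicity assessment and AE reporting are separate channels. They have separate rows in 7.1 and separate entries in 7.3. Sections 5.2 and 5.5.3 require sites to identify attributable Grade 3 or higher toxicity, with no expectedness limit, because it drives dosing. Blood pressure, creatinine and potassium are taken weekly during radiotherapy, and titration or administration forms are submitted for Weeks 1–6. Section 11.4 lists a summary of observed toxicities apart from AEs among the possible contents of DSMB reports, and 12.6 promises the DSMB both every six months. The filter is also deliberate, explained, applied to a marketed IND-exempt drug, and does not extend to deaths.

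Much of this stands, and it rules out several stronger readings that a reader might infer:

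- That these events are recorded nowhere, or are hidden from the DSMB. The visit forms and toxicity summaries may carry them, so 11.4 does not contradict 10.3.
- That the 12.7 rate is biased. It would be if built from the AE form, but 12.7 does not say that it is.
- That the serious-event definition is unused. Section 10.1.2 makes serious status a data element, and 8.3 and 10.4 refer to it. It simply does not trigger a report alone.
- That a reported 0 of 75 (exact 95% upper limit 4.8%) would falsely exclude the 11% hypotension rate in 6.1. That rate is not confined to Grade 3–4, so the two are not comparable, and a limit computed on events that were not collected has no meaning.

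The defence does not close the gap. Nothing states which terms, grades or attributions the visit forms hold, or that 12.7 draws on them. The assessment period is given in two ways. The monthly DSMC review is limited to reportable AEs in any case.

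**Conclusion.** The point holds and should be fixed. A non-fatal Grade 3–4 event related to Ramipril and classed as expected is not required on the REDCap AE form and so falls outside the monthly DSMC review. The plan meanwhile analyses related Grade 3 or higher toxicity without that restriction and without saying where the data come from.

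In reporting rules, the gap is 6 of 18 related cells. In patients, its size is unknown: about 1 to 4 of 75 if the true rate is 1% to 5%, which is assumed. The conclusion does not depend on that rate. It does depend on expectedness being read from 6.2 and the package insert, which 10.0 suggests but no section states. How often a given Grade 4 event would be classed as expected is therefore uncertain. Whether the 12.7 rate is affected depends on the unnamed source.

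**What to change.** - In 10.3 and its chart, require routine, non-expedited REDCap entry within 10 calendar days for Grade 3–4 events, and for serious events as defined in 10.2, with Possible, Probable or Definite attribution to Ramipril, whether expected or not. The chart would then cover 18 of 18 related cells.
- Leave the CTEP-AERS rules unchanged.
- In 12.7, name these records as the source for the related Grade 3 or higher rate.
- Reconcile 7.1 with 7.3 on the period of toxicity assessment.

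The cost is a short amendment and a few extra REDCap entries per site; 5.2 and 5.5.3 already ask sites to identify attributable Grade 3 or higher toxicity. Non-serious Grade 1–2 events and expected unrelated Grade 3–4 events stay exempt, so the purpose of the filter is largely kept. If the visit forms already hold graded and attributed toxicity, naming them in 12.7 could settle the analysis question, but it would not bring these events into the monthly DSMC review.
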